### 4.2. Data Analysis Plans

#### 4.2.1. General Considerations

Statistical analysis of this study will be the responsibility of Eli Lilly and Company or its designee.

Pharmacokinetic/PD analyses will be conducted on the full analysis set. This set includes all data from all randomized patients receiving at least 1 dose of the investigational product

according to the treatment the patients actually received. Safety analyses will be conducted for all enrolled patients, whether or not they complete all protocol requirements.

Summary statistics, data tabulations, and data graphs by ethnicity (Japanese and non-Japanese) will be provided as appropriate.

Additional exploratory analyses of the data will be conducted as deemed appropriate. Analyses will be fully detailed in the statistical analysis plan. Study results may be pooled with the results of other studies for population pharmacokinetic analysis purposes to avoid issues with posthoc analyses and incomplete disclosures of analyses.

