CSE	clinically significant event: a moderate to severe adverse event (AE), abnormal clinical sign, or clinical laboratory finding that may pose a risk to the well-being of the patient.
CSF	cerebrospinal fluid
ECG	electrocardiogram
EDTA	ethylene diamine tetraacetic acid
end of trial (study)	End of trial is the date of the last visit or last scheduled procedure shown in the Study Schedule for the last patient.
enroll	The act of assigning a patient to a treatment. Patients who are enrolled in the trial are those who have been assigned to a treatment.
enter	Patients entered into a trial are those who sign the informed consent form directly or through their legally acceptable representatives.
ERB	ethical review board: A board or committee (institutional, regional, or national) composed of medical professionals and nonmedical members whose responsibility is to verify that the safety, welfare, and human rights of the patients participating in a clinical trial are protected.
FCSRT-IR	Free and Cued Selective Reminding Test with Immediate Recall
FLAIR	fluid attenuation inversion recovery
GCP	good clinical practice: A standard for the design, conduct, performance, monitoring, auditing, recording, analyses, and reporting of clinical trials that provides assurance that the data and reported results are credible and accurate, and that the rights, integrity, and confidentiality of trial subjects are protected.

hERG	human ether-a-go-go-related gene
HIV	human immunodeficiency virus
IB	Investigator's Brochure: A compilation of the clinical and nonclinical data on the investigational product(s) which is relevant to the study of the investigational product(s) in human subjects.
ICF	informed consent form
ICH	International Conference on Harmonisation
informed consent	A process by which a patient voluntarily confirms his or her willingness to participate in a particular trial, after having been informed of all aspects of the trial that are relevant to the patient's decision to participate. Informed consent is documented by means of a written, signed and dated informed consent form.
interim analysis	An interim analysis is an analysis of clinical trial data, separated into treatment groups, that is conducted before the final reporting database is created/locked.

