8.2. Discontinuation

The reason for, and date of, discontinuation will be collected for all patients. All randomized patients who discontinue, regardless of whether or not they received investigational product, will have procedures performed as shown in the Study Schedule ([Attachment 1](#)).

8.2.1. *Discontinuation of Patients*

8.2.1.1. *Patients Inadvertently Enrolled*

The criteria for enrollment must be followed explicitly. If the investigator site identifies a patient who did not meet enrollment criteria and who was inadvertently enrolled, the sponsor must be notified. If the sponsor identifies a patient who did not meet enrollment criteria and who was inadvertently enrolled, the investigator site will be notified. A discussion must occur between the Lilly clinical pharmacologist or clinical research physician (CRP) and the investigator to determine whether the patient may continue in the study, with or without investigational product. Inadvertently enrolled patients may be maintained in the study and on investigational product when the investigator and Lilly clinical pharmacologist or CRP agree it is medically appropriate for that patient. The patient may not continue in the study with or without investigational product if the Lilly clinical pharmacologist or CRP does not agree with the investigator's determination it is medically appropriate for the patient to continue. The investigator must obtain documented approval from Lilly clinical pharmacologist or CRP to allow the inadvertently enrolled patient to continue in the study with or without investigational product.

8.2.1.2. *Discontinuations from Investigational Product or from the Study*

Patients will be discontinued from the investigational product and/or from the study in the following circumstances:

- enrollment in any other clinical trial involving an investigational product or enrollment in any other type of medical research judged not to be scientifically or medically compatible with this study
- investigator decision
 - the investigator decides that the patient should be discontinued from the study

- if the patient, for any reason, requires treatment with another therapeutic agent that has been demonstrated to be effective for treatment of the study indication, discontinuation from the study occurs prior to introduction of the other agent
- patient or study partner decision
 - the patient requests to be discontinued from the study
- sponsor decision

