### Figure AACD.3.1. Study Design.

## 4. A Priori Statistical Methods

### 4.1. Determination of Sample Size

Up to approximately 150 patients may be enrolled to ensure that approximately 72 patients complete the study. Cohorts 1, 2, and 3 are each planned to have a minimum of 8 patients (6 LY3002813; 2 placebo) complete the study. Cohorts 4 and 5 are each planned to have a minimum of 12 patients (9 LY3002813; 3 placebo) complete the study. Also, Cohorts 6 and 7 are each planned to have a minimum of 12 patients (9 LY3002813; 3 placebo) complete the study.

The sample size is customary for studies evaluating safety, PK, and/or PD parameters; at the conclusion of the trial, confidence intervals (CIs) for PK, PD, and cognition endpoints may be computed in order to evaluate the precision of the estimates where appropriate. Based on prior Lilly clinical trials, 6 patients randomized to each LY3002813 dose and placebo provide over 90% power to detect at least a **CCI** mean SUVr reduction of a dose compared to that of placebo without multiple comparison adjustment. Based on Fixed and Adaptive Clinical Trial Simulator (FACTS) simulations, there is over 90% success rate that at least 1 LY3002813 dose separates from placebo with a success criterion of  $\Pr(\text{mean SUV}_r \text{ reduction of LY3002813 dose} < \text{mean SUV}_r \text{ reduction of placebo}) > \text{CCI}$ . If more patients are needed to determine safety, target engagement, PK, dosing, and/or race differences, then up to a total of 10 additional patients may be added.

In order to maintain a constant accrual rate, the randomization ratio will be 6:2 in Cohorts 1, 2, and 3; randomization will progress with a 9:3 ratio in Cohorts 4 to 7. It is intended that at least 2 Japanese patients will be enrolled in each dose cohort for Cohorts 2, 4, and 6. Assuming that the cohorts will be dosed based on safety reviews, it is intended that at least 3 Japanese patients will be enrolled in each dose cohort for Cohorts 3, 5, and 7. If the number of recruited Japanese patients per cohort is fewer than 3, then the randomization will continue. Japanese patients will continue to enroll with a 2:1 randomization ratio with the cohort. Details on the randomization plan will be described in the interactive web response system (IWRS).

This ratio is based on the enrolment rate of Study AACC.

Patients who are randomized but who do not complete the 12-week safety and PET assessment may be replaced.

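### The safety set is all enrolled patients, which the protocol defines as assigned to treatment, so randomised patients who were never dosed can enter the per-dose AE and SAE denominators

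*SAP*

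**What the plan says.** The safety population is set in one sentence, identical in SAP 4.2.1 and Protocol 11.2.1: "Safety analyses will be conducted for all enrolled patients, whether or not they complete all protocol requirements". The SAP does not define enrolment. The protocol does, in its list of abbreviations and definitions: "Patients who are enrolled in the trial are those who have been assigned to a treatment". Receipt of a dose plays no part in that definition.

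The PK/PD set in the same paragraph is built differently: "This set includes all data from all randomized patients receiving at least 1 dose of the investigational product", with patients grouped by the treatment they actually received. The safety sentence has neither condition, and no other section of either document defines a dosed-only safety set.

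Protocol 8.2 allows for patients who are assigned and then not dosed: "All randomized patients who discontinue, regardless of whether or not they received investigational product, will have procedures performed". It gives no number or rate.

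The outputs that depend on the safety set are these:
- SAP 4.2.7.1 presents AE incidence for each IV dose and names no denominator of its own.
- SAP 4.4 asks for the number of participants at risk for each event term and treatment group, without defining at risk.
- SAP 4.2.7.2 reports ARIA as a shift table from predose to postdose MRI.
- SAP 4.2.7.3 models change from baseline in antibody response after dosing.

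**The concern.** Safety is a secondary objective, reported as incidence by dose. A patient who never received product cannot have an infusion reaction or any other drug-caused event, yet under the stated rule is counted below the line.

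The numerator rules make the mismatch sharper. Under Protocol 10.6.2, SAE collection starts only once the patient has both consented and received product. An earlier event is reported as serious only if the investigator thinks a protocol procedure may have caused it. Under SAP 4.4, the registry category of other AEs is limited to treatment-emergent events. For those tables an undosed patient adds to the denominator and can hardly ever add to the numerator.

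The active groups are planned at six or nine patients, so one extra patient visibly changes a percentage. The missing as-treated rule is a second, smaller gap: if a patient were given the wrong treatment, the plan does not say under which group that patient's safety data would be tabulated.

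**Working it through.** **Inputs from the documents (SAP 4.1)**
- Part A: "Cohorts 1, 2, and 3 are each planned to have a minimum of 8 patients (6 LY3002813; 2 placebo) complete the study".
- Part B: "Cohorts 4 and 5 are each planned to have a minimum of 12 patients (9 LY3002813; 3 placebo) complete the study".
- Part C: "Cohorts 6 and 7 are each planned to have a minimum of 12 patients (9 LY3002813; 3 placebo) complete the study".
- Overall: "Up to approximately 150 patients may be enrolled to ensure that approximately 72 patients complete the study".

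**The plan's own figure.** 3 × 8 + 4 × 12 = 24 + 48 = 72. Of these, 3 × 6 + 4 × 9 = 54 are active and 3 × 2 + 4 × 3 = 18 are placebo. The 72 completers are reproduced. The dose-group denominators at issue are therefore 6 and 9 active patients, within cohorts of 8 and 12.

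**Assumption.** The number of undosed patients per active group, k, is not in the documents. I take k = 0, 1 or 2.

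**Case A: undosed patients are added to the planned group.** This can happen because patients who miss the 12-week assessments may be replaced (SAP 4.1, Protocol 11.1), and a replaced patient remains enrolled. With e drug-caused events among n dosed patients, the rate is e/n and the reported rate is e/(n + k). The relative fall is k/(n + k), whatever the value of e.

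| n dosed | k | Relative fall | Example |
|---|---|---|---|
| 6 | 0 | 0 | 1/6 = 16.7%, unchanged |
| 6 | 1 | 1/7 = 14.3% | 1/6 = 16.7% becomes 1/7 = 14.3% |
| 6 | 2 | 2/8 = 25.0% | 2/6 = 33.3% becomes 2/8 = 25.0% |
| 9 | 0 | 0 | 2/9 = 22.2%, unchanged |
| 9 | 1 | 1/10 = 10.0% | 2/9 = 22.2% becomes 2/10 = 20.0% |
| 9 | 2 | 2/11 = 18.2% | 3/9 = 33.3% becomes 3/11 = 27.3% |

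**Case B: the undosed patient sits inside the planned group.** The rate among dosed patients is e/(n − k), the reported rate is e/n, and the relative fall is k/n. For k = 1 this is 1/6 = 16.7% (2/5 = 40.0% becomes 2/6 = 33.3%) or 1/9 = 11.1% (2/8 = 25.0% becomes 2/9 = 22.2%).

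**Direction of the active-placebo comparison.** Placebo groups are two or three patients per cohort. One undosed patient added to a placebo group of two turns 1/2 = 50.0% into 1/3 = 33.3%. If the active group shows 2/6 = 33.3%, the difference moves from 33.3 − 50.0 = −16.7 points to 33.3 − 33.3 = 0, which makes the drug look worse by comparison. An undosed patient in the active group pulls the other way for drug-caused events.

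**The case against.** The best case against is that this is a wording gap whose effect may be nil. Screening, MRI and PET come before the predose visit at a nominal Day −4, with dosing on Day 1. If assignment happens at about that visit, little time is left in which to drop out undosed, although the visit's timing is marked approximate. The shift is also small beside the sampling error: exact 95% intervals are 0.4% to 64.1% for 1/6 and 0.4% to 57.9% for 1/7. AEs are listed individually, and discontinued patients are identified with the extent of their participation, so an undosed patient would be visible. Most of the stopping criteria in Protocol 8.2.1.3 count patients and do not use a rate, and the escalation reviews count dosed patients. All of this stands, and it limits the weight of the point. It does not change what the rule says or supply a reason to prefer it.

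Four stronger readings are tempting, and the documents do not support them:
- **ARIA rates are diluted.** The shift table compares predose with postdose MRI, and a never-dosed patient has no postdose scan. An early-discontinuation MRI exists, but nothing says it would count as postdose. The text is silent, so dilution is not established.
- **The antibody model is diluted.** It uses change after dosing, a value that an undosed patient does not have.
- **The bias always favours the drug.** Undosed placebo patients lower the comparator rate. In addition, AEs are recorded from consent and include procedure-related events, and SAP 4.2.7.1 sets apart only symptoms that arise before randomisation. An undosed active patient with a procedure-related event after randomisation would raise the all-cause rate, for example from 1/6 = 16.7% to 2/7 = 28.6%.
- **The gap between 150 and 72 shows how many will be undosed.** The difference of 150 − 72 = 78 covers non-completion of every kind, and the replacement rule also covers patients who were dosed and then dropped out. Neither estimates the number never dosed.

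**Conclusion.** The point holds as a defect in a stated rule. As written, the safety set includes patients who were assigned and never dosed, lacks an as-treated condition, and differs on both counts from the PK/PD set in the same paragraph. Because SAEs and treatment-emergent events are largely confined to dosed patients, numerator and denominator do not match.

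The size depends on a count that the documents do not give. It is zero if everyone assigned is dosed. With one undosed patient added to an active group, the incidence of drug-caused events falls by 14.3% relative (n = 6) or 10.0% relative (n = 9). With two added, it falls by 25.0% or 18.2%. These figures assume that the undosed patients contribute no events. The direction is fixed only for drug-caused rates within an active group. For the active-placebo difference, and for all-cause rates that include procedure events, it can go either way. No effect on the ARIA shift table or the antibody model is claimed.

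**What to change.** In SAP 4.2.1 and Protocol 11.2.1, replace the safety sentence with a defined set: all randomised patients who received any amount of investigational product, analysed by the treatment actually received. Add that events in randomised but undosed patients are listed separately, so that procedure-related events are not lost. In SAP 4.2.7.2, state that the ARIA shift table uses dosed patients with at least one postdose MRI.

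This is a free improvement. It takes a few lines of text, with no new data, visits or patients. Fixing the denominator in advance also prevents it from being chosen once it is known who was dosed.

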#### **4.2.2. Study Participant Disposition**

All patients who discontinue from the study will be identified, and the extent of their participation in the study will be reported. If known, a reason for their discontinuation will be given.

For all Screening entries, compute a summary count table to enumerate the reasons for screen failure according to criteria as defined by the following inclusion and exclusion evaluations. Essentially, summarize visits 1,2, and 3.

At Visit 1, patients will undergo the screening tests outlined in the Study Schedule in Protocol Attachment 1. Upon fulfilling the screening criteria at Visit 1, the patient will undergo a screening MRI (Visit 2) and then a screening florbetapir PET scan (Visit 3), sequentially, provided that the MRI criteria are met before the PET scan occurs. If the patient's eligibility is confirmed by a positive florbetapir PET scan, then this scan serves as their baseline PET scan. Patients may undergo some or all of the predose testing, including cognitive testing and LP as an outpatient or inpatient (Visit 4). Cognitive testing requires a minimum of 4 hours rest between the Alzheimer's Disease Assessment Scale – Cognitive Subscale (ADAS-cog) and Neuropsychological Test Battery (NTB) to avoid test fatigue; ideally, cognitive testing should occur before lumbar puncture (LP) if on the same day, and LP should occur no closer than 24 hours before dosing. However, LP could be performed as a separate visit, and cognitive testing can be performed after a minimum of 24 hours has passed after performing the LP, and patient must be free from any post-LP headache. Patients should be admitted on Day 1, but may be admitted to the clinical research unit (CRU) on Day -1 (the day before the first dosing day).

Patients are eligible for enrollment in the study only if they meet all of the following criteria

- [1] Patients must meet all the research disease diagnostic criteria for MCI due to AD or mild to moderate AD below, consistent with NIAAA research diagnostic guidelines (Albert et al. 2011; McKhann et al. 2011).
  - a) gradual and progressive change in memory function reported by patients or informants over more than 6 months

- b) objective evidence of significantly impaired episodic memory characteristic of hippocampal dysfunction on testing: Free and Cued Selective Reminding Test with Immediate Recall (FCSRT-IR):  $\leq 24$  for free recall or  $\leq 46$  for total recall (The episodic memory impairment can be isolated or associated with other cognitive changes at the onset or as the disease advances.) (Auriacombe et al. 2010; Grober et al. 2010)
- c) Clinical Dementia Rating (CDR)=0.5 to 2 and memory box score  $\geq 0.5$
- d) Mini-Mental State Examination (MMSE) score 16 to 30
- e) positive florbetapir scan (central read)
- f) Geriatric Depression Scale (GDS; Sheikh and Yesavage 1986) score  $< 6$  (on the staff-administered short form)

[2] men or nonfertile women, at least 50 years of age. Nonfertile is defined as hysterectomy and/or bilateral oophorectomy, or amenorrhea for at least 1 year.

[3] have a caregiver/study informant who provides a separate written informed consent to participate. The caregiver/study informant is required to accompany the patient for signing consent, all dosing days and for all days that the Columbia Suicide Severity Rating Scale (C-SSRS)/Self-Harm Follow-Up (SHSF) and cognitive and functional scales are administered. If the caregiver/study informant is not able to accompany the patient in person because of an unavoidable circumstance, he/she must be available by telephone to answer questions regarding AEs and concomitant medications, and to answer the questions for the caregiver portions of the C-SSRS/SHSF. If any caregiver/study informant familiar with the study cannot continue, 1 replacement is allowed. More than 1 replacement may be allowed per investigator's discretion. The replacement(s) will also need to sign a separate written informed consent on the first visit he/she accompanies the patient to participate. The caregiver(s)/study informant(s) must be in frequent contact with the patient (defined as at least 10 hours per week), willing to accompany the patient to the office and/or be available by telephone at designated times, and willing to monitor administration of prescribed medications.

[4] have adequate premorbid literacy, vision, and hearing for neuropsychological testing in the opinion of the investigator

[5] have given written informed consent approved by Lilly and the ethical review board (ERB) governing the site

[6] are reliable and willing to make themselves available for the duration of the study and are willing to follow study procedures

Patients will be excluded from study enrollment if they meet any of the following criteria:

- [7] are investigator site personnel directly affiliated with this study and their immediate families. Immediate family is defined as a spouse, parent, child, or sibling, whether biological or legally adopted.
- [8] are Lilly employees or employees of third-party organizations (TPOs) involved with the study
- [9] have participated, within the last 30 days (for sites in Japan, 4 months) of screening, in a clinical trial involving an investigational product (other than the investigational product used in this study). If the previous investigational product has a long half-life, 3 months (for sites in Japan, 4 months) or 5 half-lives (whichever is longer) should have passed.
- [10] are persons who have previously completed or withdrawn from this study. This exclusion criterion does not apply to patients who are allowed to re-screen before randomization.
- [11] are persons who have previously participated in a study investigating LY3002813 and received active treatment with LY3002813
- [12] are persons who have previously participated in a study with active and/or passive immunization against A $\beta$  (not including LY3002813)
- [13] have had gamma globulin therapy within the last 6 months
- [14] have allergies to either humanized monoclonal antibodies, diphenhydramine, epinephrine, or methylprednisolone
- [15] have a history of clinically significant multiple or severe drug allergies or severe posttreatment hypersensitivity reactions (including but not limited to erythema multiforme major, linear IgA dermatosis, toxic epidermal necrolysis, and/or exfoliative dermatitis)
- [16] have known allergies to LY3002813, related compounds, or any components of the formulation, or history of significant atopy
- [17] have a clinically significant abnormality in the 12-lead ECG, including left bundle branch block, second or third degree heart block, or Bazett corrected QT interval  $\geq 470$  msec for male patients or  $\geq 480$  msec for female patients.
- [18] have an unacceptable blood pressure and pulse rate, as determined by the investigator (Note: patients may be on a stable hypertension medication.)
- [19] show evidence of suicidal ideation as assessed by the C-SSRS
- [20] show evidence of significant active neuropsychiatric disease; depression as assessed by medical history, examination, or GDS
- [21] show evidence of human immunodeficiency virus (HIV) infection and/or positive human HIV antibodies
- [22] show evidence of syphilis and/or are positive for syphilis test
- [23] are women who are lactating

- [24] have used stable medical therapy for less than 2 months for any concurrent medical condition that is not exclusionary
- [25] have donated blood of more than 500 mL within the last 30 days before dosing. For patients in Japan: have donated blood  $\geq 400$  mL in the last 3 months (male patients) or in the last 4 months (female patients), or any blood donation (including apheresis) within the last 1 month, or total volume of blood donation within 12 months is 1200 mL (male patients) or 800 mL (female patients) at screening.
- [26] have an average weekly alcohol intake that exceeds 21 units per week (male patients up to age 65) and 14 units per week (male patients over 65 and female patients), or are unwilling to stop alcohol consumption 48 hours before dosing until each discharge from the CRU (1 unit=12 oz or 360 mL of beer; 5 oz or 150 mL of wine; 1.5 oz or 45 mL of distilled spirits)
- [27] have a known history of alcohol or drug abuse (as defined by the Diagnostic and Statistical Manual, Fourth Edition, Text Revision) within 2 years of enrolling or a positive result regarding use of illicit drugs on the drug screening test
- [28] have current serious or unstable illnesses including hepatic disease (cirrhosis, hepatitis A, B, or C [presence of antibody to hepatitis B surface antigen in the setting of hepatitis B immunization is not an exclusion; the presence of hepatitis C antibody a normal liver function tests and a negative hepatitis C polymerase chain reaction is also not an exclusion]); renal, gastroenterologic, respiratory, cardiovascular disease (active ischemic heart disease [stable or unstable angina], intermittent atrial fibrillation); endocrinologic disease (stable non-insulin-dependent diabetes or stable thyroid disease is not an exclusion); neurologic disease (other than AD); psychiatric disease (including suicidal ideation); immunologic, infectious (HIV, tuberculosis, Lyme, or hematologic disease (including transfusion within past year); or other conditions that, in the investigator's opinion, could interfere with the analyses of safety in this study.
- [29] have a history of uncontrolled asthma, significant autoimmune disease (rheumatoid arthritis, systematic lupus erythematosus), hereditary angioedema, or common variable immune deficiency
- [30] have any contraindications for MRI, including claustrophobia or the presence of contraindicated metal (ferromagnetic) implants/cardiac pacemaker
- [31] have a head MRI (central read) demonstrating either greater than 4 cerebral microhemorrhages on T2\*-weighted gradient-echo sequence (regardless of their anatomical location), or a single area of superficial siderosis, or prior evidence of macrohemorrhage, or any other major intracranial pathology except: atrophy, meningiomas without mass effect, benign pituitary microadenomas, and/or mild to moderate white matter hyperintensities on fluid attenuation inversion recovery (FLAIR)

- [32] have a history of intracranial hemorrhage; cerebrovascular aneurysm or arteriovenous malformation; or carotid artery occlusion, stroke, or epilepsy
- [33] have criteria that would preclude an LP, such as allergy to all local anesthetics (such as lidocaine); have a local infection at the site of the LP; have  $\leq 100$  GI/L ( $100,000/\text{mm}^3$ ) platelets, clinically significant coagulation abnormality, or significant active bleeding; treatment with an anticoagulant; or treatment with 2 or more antiplatelet agents or other drugs that affect coagulation or platelet function within 14 days before lumbar catheter insertion
- [34] show abnormalities in lumbar spine previously known or determined by screening lumbar x-ray (if conducted)
- [35] in the opinion of the investigator have a history of clinically significant back pain, back pathology, and/or back injury (for example, degenerative disease, spinal deformity, or spinal surgery) that may predispose to complications or technical difficulty with LP
- [36] have medical or surgical conditions in which LP is contraindicated
- [37] have poor venous access that would preclude IV drug delivery or multiple blood draws
- [38] have screening clinical laboratory test results with unacceptable deviations that are judged to be clinically significant by the investigator
- [39] have a history within the past 5 years of a primary or recurrent malignant disease with the exception of resected cutaneous squamous cell carcinoma in situ, basal cell carcinoma, cervical carcinoma in situ, or in situ prostate cancer with a normal prostate-specific antigen after resection
- [40] are being monitored for radiation due to occupational exposure to ionizing radiation, or exposure to ionizing radiation within last 12 months from an investigational study
- [41] in the opinion of the investigator or sponsor, are unsuitable for inclusion in the study.

